The practice of genetic medicine is changing as genetic discoveries are translated into new tests for an increasing number of health indications. In fact, the prevalence of high-risk individuals who are at risk for hereditary cancer has been rising due to new testing strategies. This has placed enormous pressure on the hospitals and clinics providing care for high-risk patients. Coupled with the healthcare system's need for greater efficiency, the traditional genetic clinic-based practice has become untenable. Barriers and challenges include low numbers of trained genetic workforce, lack of integrated FHH platforms for patients and physicians, and long wait times for available clinic appointments. Further, while cancer syndromes are seen across all groups, gaps in care exist as underserved populations are often not recognized and referred for care.

MeTree is a computer platform that has been developed by researchers at Duke University that electronically collects FHH information for hereditary cancer syndromes and other health conditions directly from the patient. MeTree then calculates hereditary cancer risks for the patient and creates a personalized patient report and evidence-based clinical decision support for the provider. In previous studies, MeTree demonstrated improvements in the identification of those at risk and highlighted ongoing challenges particularly around undergoing genetic counseling and testing, and awareness of risk. Co-investigators from Duke/MeTree collaborate on this grant.

2. Rationale and Specific Aims

SA1. Deploy a care delivery model that will facilitate systematic risk assessment for hereditary cancers in diverse clinical environments.

- Up to 3,500 participants will be enrolled and complete the MeTree FHH risk assessment
- Deploy in 2 academic medical centers; Vanderbilt University Medical Center (VUMC) and Meharry Medical College (MMC)
- Assess participants perceptions using online survey and qualitative semi-structured interviews

SA2. Improve access to genetic healthcare providers for participants at risk for hereditary cancer syndromes.

- 300 high risk participants in the VUMC Hereditary Cancer Clinic will be enrolled
- Extend clinic capacity by lessening the need for in-clinic family history collection and basic counseling
- Expand reach of clinic by using telephone and video genetic counseling; referral to specialists

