Once data entry in MeTree is complete all participants will receive a personalized patient report within the platform outlining their familial and genetic risk status the included medical conditions according to current evidence-based guidelines. Participants' providers will be notified via one of several methods (email without PHI, EPIC messaging, or an alert) that their patient has a MeTree clinical decision support report available in the medical chart (accessible via a SMART link). Outside providers will receive an email or letter. The templates for these messages is located in Appendix I. The process to upload the MeTree report and provide accessibility to providers is approved by the Medical Forms Committee and the Center for Health Information Management (CHIM) Committee.

As previously stated, in Aim 2 participants who are identified as at high genetic risk (n=300) will be contacted by the study nurse (as part of their standard of care) to schedule a genetic counseling appointment (Appendix J, High risk patient email). The number and length of genetic counseling appointments will be recorded in order to evaluate the change in clinic capacity for those with a pre-recorded FHH in the MeTree platform as compared to routine patients who have not participated in the study and completed MeTree. The frequency of genetic testing and outcomes of the testing will also be recorded in REDCap from data collection in the Hereditary Cancer Clinic at VUMC.

[figure not shown]
To analyze the time saved by completing MeTree prior to a clinic visit, the study team will perform a retrospective review of control patients, selected by the study team, to assess the amount of time in clinic with the genetic counselors. This will be done through time stamps in eStar and chart review. Control patients will not be a part of the study, nor will their information be shared with anyone. The study team will only review for time spent in clinic versus the study participants' clinic visits.

Additionally, genetic counselors who see participants from this study will be surveyed to better understand their perspective of the use of MeTree. This portion of the study will be in a separate IRB.

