### 3. Analytical Population(s)

- a. **Reach population:** defined as the participants who were invited to use MeTree (completed baseline surveys and clicked link to use MeTree)
- b. **Effectiveness population:** defined as the participants who completed MeTree and had a clinical decision support risk report generated.
- c. **Genetic counseling population:** The genetic counseling population includes participants who completed MeTree, received a genetic counseling recommendation and completed the genetic counseling appointment. A random selection of non-study participants with genetic counseling appointments at the same clinic and in the same time frame will be selected, 1:1.
- d. See the protocol paper for additional details of these populations:  
<https://www.sciencedirect.com/science/article/pii/S1551714424002970#f0010>
- e. Study participants had to meet the following inclusion and exclusion criteria to be enrolled in the FOREST study:
  - i. Inclusion
    1. Site: VUMC, MMC
    2. Demographics: Age 18 years or older
    3. Able to read and communicate in English
    4. Willing and able to use the internet to report FHH information
    5. Current user of patient portal (VUMC specific)
  - ii. Exclusion
    1. Not a patient at VUMC or MMC sites
    2. Diagnosed with a terminal illness
    3. Unable to speak/read English
    4. Unwilling or unable to use the Internet to report their FHH information
    5. Report previous genetic testing and/or counseling through the VUMC Hereditary Cancer Clinic
- f. Analyses involving EHR -related information will be restricted to VUMC participants due to the specificity of the EHR-based outcomes.

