### 3. Secondary Endpoint 1: EHR-based identification of hereditary risk pre- and post-MeTree

- a. **Hypothesis:**

- i.  $H_0$ : MeTree has no impact on identification of patients at high risk for hereditary cancer
- ii.  $H_A$ : MeTree impacts the identification of patients at high risk for hereditary cancer

- b. **Analysis:** Descriptive statistics (counts and percentages) will be used to describe the EHR-based indication for increased cancer risk (Variable 7: presence of a personal or family history codes) for the two study time periods: pre-study consent period (T0-T1) to the post-study consent period (T1-T2) within the effectiveness population. Contrast the EHR-based determination of high risk for cancer (Variable 7), between the pre-study consent period (T0-T1) to the post-study consent period (T1-T2) using the McNemar test for paired observations, test statistic and p-value will be reported.

**4. Secondary Endpoint 2:** Genetic counseling appointment length for participants who used MeTree and for randomly selected patients from the same clinic who did not use MeTree.

a. **Hypothesis:**

- i.  $H_0$ : Using MeTree prior to genetic counseling has no impact on genetic counseling appointment length
- ii.  $H_A$ : Using MeTree prior to genetic counseling affects genetic counseling appointment lengths

b. **Analysis:** Descriptive statistics (mean, standard deviation, median and IQR or counts and percentages) will be used to summarize appointment lengths by intervention group. Differences in genetic counseling appointment length between intervention groups will be assessed using the Wilcoxon rank sum test, p-value will be reported

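### Secondary Endpoint 2 compares tool-flagged participants with routine clinic patients matched only on clinic and period, without adjustment, so case mix and new-versus-return status can bias the estimated effect of MeTree on appointment length

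*SAP*

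**What the plan says.** **MeTree group.** SAP II.3.c defines it as "participants who completed MeTree, received a genetic counseling recommendation and completed the genetic counseling appointment". Protocol section 5 describes the route to the clinic: "participants who are identified as at high genetic risk (n=300) will be contacted by the study nurse".

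**Control group.** SAP II.3.c: "A random selection of non-study participants with genetic counseling appointments at the same clinic and in the same time frame", drawn 1:1. Protocol section 5 makes the comparison with routine patients ("as compared to routine patients who have not participated in the study and completed MeTree") and describes a "retrospective review of control patients, selected by the study team". It confines that review to time in clinic.

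**Eligibility.** The criteria in SAP II.3.e are stated for study participants. They exclude terminal illness, inability to speak or read English, inability or unwillingness to use the internet, and self-reported earlier counseling or testing at the VUMC Hereditary Cancer Clinic. No corresponding limits are stated for controls.

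**Outcome and analysis.** SAP III.2.b defines the outcome only as appointment length; it does not distinguish first from return visits or separate visit types. SAP IV.4: "Differences in genetic counseling appointment length between intervention groups will be assessed using the Wilcoxon rank sum test". SAP IV.1.b describes and tests demographic differences between the groups but plans no adjustment.

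**Visit type.** Aim 2 in Protocol section 2 includes this element: "Expand reach of clinic by using telephone and video genetic counseling; referral to specialists".

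**The concern.** The hypothesis in SAP IV.4 is causal: that using MeTree before the visit changes its length. Protocol section 5 likewise states the purpose as measuring time saved. The two groups, however, come to the clinic by different routes. One is found by screening a general patient population; the other is the clinic's ordinary caseload. Drawing controls at random makes them representative of that caseload. It does not make them comparable with screen-detected patients, and a larger sample does not remove the difference.

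The eligibility list adds an asymmetry that can be read directly from the text. A patient who reports earlier counseling or testing at this clinic cannot be in the MeTree group but can be drawn as a control.

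Any patient or visit characteristic that affects appointment length and is distributed differently between the groups will appear as a MeTree effect, or will offset a real one. This is the SAP's only inferential test of the Aim 2 capacity question.

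**Working it through.** **1. What the documents fix.** Protocol section 8 derives its minimum sample from 150 counseled participants, a 10% identification rate and a 50% follow-up rate:

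150 / (0.10 × 0.50) = 3,000, which agrees with the stated minimum.

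The 150 itself cannot be rebuilt, because no effect size, SD or power is given for appointment length. At 150 per group (1:1) and two-sided 0.05, the detectable difference is (1.96 + z) × √(2/150):

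- 80% power: (1.96 + 0.842) × 0.1155 = 0.32 SD
- 90% power: (1.96 + 1.282) × 0.1155 = 0.37 SD

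Allowing for the rank-sum efficiency of 0.955, these become 0.33 and 0.38 SD. The 0.05 level is stated in the protocol for its primary endpoint and is assumed here.

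**2. Which features are balanced by design.**

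| Feature | MeTree group | Controls | Balanced by design? |
|---|---|---|---|
| Clinic, calendar period | Hereditary Cancer Clinic | same | yes |
| Route to clinic | tool flag, study contact | routine patients | no |
| Earlier counseling or testing here | excluded if reported | not restricted | no |
| Terminal illness, language, internet use | restricted | not restricted | no |
| Personal cancer history | not restricted | not restricted | not controlled; mix unknown |
| Visit type | telephone and video planned in Aim 2 | not stated | not controlled; mix unknown |

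**3. False rejection when MeTree has no effect.** All inputs are assumptions: 150 per group, SD 15 minutes within class, one class of patients with visits d minutes longer, making up 20% of the MeTree group and a share p of controls.

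Spurious difference = d × (p − 0.20).
Standard error = √{[2 × 15² + d² × (0.20 × 0.80 + p(1 − p))] / 150}.

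For d = 10:

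- p = 0.30: difference 1.0 minute; SE = √{[450 + 100 × (0.16 + 0.21)] / 150} = 1.80; z = 0.55; rejection about 8-9%. Simulated rank-sum test: about 8%.
- p = 0.50: difference 3.0 minutes; SE = √{[450 + 100 × (0.16 + 0.25)] / 150} = 1.81; z = 1.66; rejection about 38%. Simulated: 34-38% across runs.
- p = 0.70: difference 5.0 minutes; SE = 1.80; z = 2.77; rejection about 79%. Simulated: 78-80%.

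Simulated rejection by class difference d:

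| Class share, MeTree vs controls | d = 5 min | d = 10 min | d = 15 min |
|---|---|---|---|
| 20% vs 30% | 6% | 8% | 12-13% |
| 20% vs 50% | 13-14% | 34-38% | 65-66% |
| 20% vs 70% | 27-29% | 78-80% | 97-98% |

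A van Elteren test stratified on the class held about 5% in all six scenarios of the last two rows.

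**4. Bias in the other direction.** Suppose MeTree truly saves 0.32 SD, no participant visit is a return visit, and 20% of control visits are return visits that are shorter by s:

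- s = 0.5 SD: apparent saving 0.32 − 0.20 × 0.5 = 0.22 SD; power falls from about 80% to about 45-48%.
- s = 1 SD: apparent saving 0.32 − 0.20 × 1 = 0.12 SD; power about 18-19%.

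The 20% share and both values of s are assumptions.

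**The case against.** The strongest reply is that this is one secondary endpoint in a pragmatic study. Controls share the clinic and calendar period, demographics are compared, and the size of any bias depends wholly on assumed imbalances. That last point stands: with a 10-point imbalance and a 5-minute class difference, rejection is 6%, barely above nominal. The SAP also refers to a published protocol paper for more on these populations. I could not check it, and it may restrict controls further.

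A reader might also infer more than the documents support:

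- **That visit type is confounded with MeTree.** Telephone and video counseling are planned, but nothing says controls are seen only in person or that the mix differs. Patients of the same clinic in the same period may have the same options. Visit type is a possible confounder, not a shown imbalance.
- **That MeTree patients are unaffected by cancer.** Only terminal illness is excluded, and the SAP itself counts personal-history codes among participants. Affected status is unknown in both groups.
- **That the protocol and SAP contradict each other on control selection.** The protocol says who selects and the SAP says how. This is an ambiguity worth closing, not a clear conflict.
- **That the bias favors MeTree, or that nothing can be learned from Aim 2.** The net direction is unknown, and Aim 2 also records the number of appointments and genetic testing.

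None of this answers the central point. The groups are defined differently, eligibility limits are stated for one side only, and the planned test adjusts for nothing.

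**Conclusion.** The concern holds in a bounded form. Followed exactly, SAP II.3.c and IV.4 can give a biased answer to the causal question they pose. The best-documented asymmetry is that patients with earlier counseling or testing at this clinic can appear among controls only. Uncontrolled referral indication and personal cancer history follow from the group definitions as open risks; visit type is a further possibility.

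The size cannot be fixed from the documents. With 150 per group, SD 15 minutes, no MeTree effect and a 10-minute class difference, false rejection runs from about 8% (10-point imbalance) to about 34-38% (30-point imbalance). A real saving could equally be masked. As written, neither a significant difference nor its absence could be ascribed to MeTree with confidence. The change should be made, but it concerns a secondary endpoint and leaves the primary one untouched.

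**What to change.** - **SAP II.3.c.** Restrict controls to first visits by patients who meet those participant eligibility criteria that can be read from the chart, including no earlier counseling or testing at this clinic. State that the participant visit analyzed is likewise the first. Within the same clinic and time frame, draw controls at random within strata of personal cancer history (yes/no) and visit type (in person, telephone, video).
- **SAP IV.4.** Make a stratified (van Elteren) rank-sum test on those strata the main analysis and keep the unadjusted test as a sensitivity analysis.
- **Protocol section 5.** State that control selection is random. Widen the control chart review, now limited to time in clinic, to include visit status (first or return), visit type and personal cancer history.

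**Cost.** A small protocol amendment, since the present text does not allow these fields to be read for controls, and a few more chart fields per control. Some strata may be sparse. The strata do not capture reason for referral, so screen-detected and referred patients may still differ within them; the SAP should state this as a limitation.

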We will use a case-control design for statistically analyses. Cases are defined as the study participants who have completed the MeTree tool (intervention). We will utilize data from the Hereditary Cancer Clinic registry (IRB # 141203) to fine patients identified at risk of a hereditary cancer syndrome in the usual care (control) and intervention conditions. The control condition utilizes historical data from the participants prior to their enrollment date in FOREST to determine the number and proportion of participants who would be identifiable as at risk without the implementation of MeTree. We believe this is the most effective method to analyze the MeTree platform's effect on hereditary cancer testing and outcomes. Power calculations estimate a sample size of up to 3,500 (minimum of 3,000) is needed to produce statistically significant results.

In the graph below, the blue line represents 90% power to detect the primary endpoint with a p-value of 0.05, the green line, 85% power, and the red, 80% power. The x-axis represents how many participants are identified as being at high risk by MeTree.

In prior studies of primary care populations, on average 20% were newly found to be at high risk (had not previously identified). However, in order to accommodate differences in a population that has a proactive hereditary cancer clinic, we used a lower estimate of 10% for the power analyses. Thus at 10% risk identification and 95% power we estimated that we would need at a minimum 1,000 participants for a single site and 2,000 participants total to detect differences in identification at the 2 sites (Meharry and Vanderbilt). In addition, these participants flow into aim 2. Based on power analysis to detect an increase in clinic capacity, we need to have 150 high risk patients who complete MeTree in Aim 1 to see a genetic counselor in the hereditary cancer clinic at Vanderbilt. At a 10% identification rate and a 50% follow up rate (estimate based on literature review and the clinic's attendance rate), a minimum of 3,000 participants will need to complete MeTree in Aim 1. We are therefore enrolling 3,000-3,500 participants for this study.

Data elements considered for this analysis:

Primary Endpoint: Participant designated as high risk for cancer.

Assessment pre: chart review (any indicator prior to MeTree, not time-frame dependent)

Assessment post: MeTree report (measured when the report is generated, independent of amount of follow-up time)

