## 3. Handling of Missing Data

Data will be analyzed as captured in the redcap surveys and in the MeTree database. Missing data will not be imputed. In the MeTree relative conditions data, the absence of a condition will be assumed to be “no” if the health history is not set to “unknown.” If health history is unknown, the condition will be set to “NA.” Analysis reports will be programmatically generated from processed MeTree data cuts.

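### Controls for the appointment-length comparison are not held to the eligibility rules that define the MeTree group, so the two groups are selected differently

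*SAP*

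**What the plan says.** SAP II.3.c defines both sides of the comparison. The MeTree side consists of "participants who completed MeTree, received a genetic counseling recommendation and completed the genetic counseling appointment". The control side is defined in the next sentence, with a 1:1 ratio: "A random selection of non-study participants with genetic counseling appointments at the same clinic and in the same time frame".

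The eligibility list in II.3.e is addressed to one side only: "Study participants had to meet the following inclusion and exclusion criteria to be enrolled in the FOREST study". It requires age 18 or older, English, willingness and ability to use the internet and, at VUMC, current portal use. It excludes terminal illness and reported previous testing or counseling through the VUMC Hereditary Cancer Clinic.

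Protocol section 5 (Study Procedures) describes the comparators as routine patients chosen by the study team. Their time with the counselors is reviewed retrospectively from eStar time stamps and charts. It adds no eligibility condition for them.

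For the analysis, SAP IV.4 states: "Differences in genetic counseling appointment length between intervention groups will be assessed using the Wilcoxon rank sum test". SAP IV.1.b compares the demographics of the two groups but plans no adjustment. SAP III.3 adds: "Missing data will not be imputed".

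**The concern.** Group membership is not randomized, so the comparison is only as good as the rule that picks the controls. As written, several kinds of visit can occur among controls and cannot, or should not, occur among participants: return visits by patients already counseled or tested at this clinic, visits by minors, visits through an interpreter, and visits by patients with a terminal illness. Each could plausibly differ in length for reasons unrelated to MeTree. The criterion on previous counseling or testing matters most, because it bears directly on the type of visit.

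Appointment length is the SAP's only tested measure of the time-saving claim behind Aim 2. A difference produced by selection would be read as an effect of MeTree, and a real effect could equally be hidden.

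**Working it through.** **The plan's own figure.** Protocol section 8 needs 150 high-risk participants to see a counselor, with 10% identified and 50% following up: 150 / (0.10 × 0.50) = 3,000, as stated. The 150 itself cannot be rebuilt, because no effect size, SD, alpha or power is given for appointment length.

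**The two selection rules side by side.**

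| Condition | MeTree group | Controls |
|---|---|---|
| Same clinic | yes | yes |
| Same time frame | yes | yes |
| Age 18 or older | required | not stated |
| English | required | not stated |
| Internet use; portal use (VUMC) | required | not stated |
| No terminal illness | required | not stated |
| No reported previous testing or counseling at this clinic | required | not stated |
| Visit completed | required | not stated, but implied by the protocol's review of time in clinic |

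No later step restores the balance: the test is unadjusted and no rule for replacing a drawn control is given.

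**Illustration of size.** None of these inputs except the 150 comes from the documents. Assume 150 per group (the control number follows from 1:1), lengths normal with mean 60 and SD 20 min, no MeTree effect, and a two-sided 0.05 rank-sum test. A fraction f of controls falls outside II.3.e, and their visits differ by e minutes. The mean of the control group then moves by f × e; for example, 0.10 × 30 = 3 min, or 3 / 20 = 0.15 SD. Rejection rates from 4,000 simulated trials per setting, with the outside visits longer:

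| f | e = 20 min | e = 30 min |
|---|---|---|
| 5% | 7.2% | 8.5% |
| 10% | 12.1% | 18.4% |
| 15% | 21.0% | 35.3% |

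The simulation error is at most √(0.353 × 0.647 / 4,000) = 0.8 percentage points. With the sign of e reversed, the rates are the same within that error and the rejections go the other way. If 10% of controls have visits 30 min longer and another 10% have visits 30 min shorter, the two cancel and the rate returns to about 5%.

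**Scale.** With 150 per group, the difference detectable with 80% power is (1.960 + 0.842) × √(2/150) = 0.323 SD, or 0.323 × 20 = 6.5 min under the assumed SD. The shifts in the table run from 0.05 × 20 = 1 min to 0.15 × 30 = 4.5 min, so the larger ones are a sizeable part of the effect that such a study could detect.

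**The case against.** The strongest reply is that the size of the problem is assumed. No passage says that this clinic sees minors, interpreter-mediated or terminally ill patients, how many it sees, or how long their visits last. That stands. A reader might infer that the bias favors MeTree, on the view that the excluded visits run longer. The documents do not support this: if return visits are shorter, the bias runs against MeTree, and opposite differences can cancel.

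A reader might also infer that many drawn controls would be missed appointments with no length, and take the attendance rate from the protocol's planning figure, "and a 50% follow up rate (estimate based on literature review and the" clinic's attendance. That does not hold either. The figure covers the path from a MeTree flag to a counseling visit among participants, not attendance at routine appointments already booked. Moreover, the protocol reviews controls for time spent with counselors, from time stamps and charts, so attended visits are the natural reading. What remains is a missing word in the SAP.

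The protocol names routine patients as the comparator, and for a question about clinic capacity an unrestricted comparator can be defended. This has some force. However, SAP IV.4 states its hypothesis as the effect of using MeTree on appointment length, and that needs groups that are otherwise alike.

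Finally, II.3.d refers to a published protocol paper for more detail on these populations. It was not available here and may restrict the controls. If it does, the SAP should state the restriction.

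**Conclusion.** The concern holds as a difference in selection rules. Participants are screened on II.3.e and controls are not, and the unadjusted test does not correct for it. The size and direction of any bias are unknown. The range of about 7% to 35% false rejections shows what modest differences could do. It rests wholly on the assumed fractions (5% to 15%), visit differences (20 to 30 min) and SD (20 min), and is not an estimate for this clinic. The missing completed-visit condition for controls is a minor clarification. This is a cheap improvement to a secondary endpoint and leaves the primary endpoint untouched.

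**What to change.** Amend SAP II.3.c so that controls are drawn at random from non-study patients who have a completed genetic counseling appointment with a recorded length, at the same clinic and in the same time frame, and who meet the II.3.e criteria that the record can show:

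- age 18 or older;
- English, with no interpreter;
- no previous testing or counseling at this clinic;
- active portal account, for the VUMC comparison;
- no terminal illness, where this is recorded.

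Replace any draw that fails until 1:1 is reached. State in the SAP that willingness to use the internet cannot be checked for controls, and that terminal illness may be incompletely recorded.

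Amend the control-review text in Protocol section 5 in two ways. It should allow these fields to be read, since it now limits the review to time in clinic. It should also reconcile selection by the study team with the SAP's random selection.

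Cost: SAP wording, a filter before the draw and a small protocol change on what is read from the charts of people outside the study. Control selection is retrospective, so no one needs to be contacted or enrolled. The control pool becomes smaller, and the result applies to study-eligible patients rather than to all routine patients. The filter does not remove the difference in referral route (MeTree recommendation versus routine referral), which should be reported as a limitation.
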